## **Introduction**

Gestational diabetes mellitus (GDM) is a prevalent condition that affects women across the globe (1). It can lead to a range of complications for both the mother and the baby. The mother may be at a higher risk of developing type 2 diabetes and premature cardiovascular disease, while the baby may experience macrosomia, obesity, hypoglycemia, diabetes, hypertension, and cardiovascular disease in their youth and adulthood (2,3). Early detection of gestational diabetes mellitus (GDM) is crucial to avoid its consequences. In 2010, the International Association of Diabetes and Pregnancy Study Groups (IADPSG) recommended a 2-hour, 75-gram oral glucose tolerance test (OGTT) to diagnose GDM in all pregnant women who did not have a history of overt diabetes during the 24th-28th weeks of pregnancy (4). The oral glucose tolerance test (OGTT) is considered to be the most reliable method, but it can be time-consuming, has poor reproducibility, and is often poorly tolerated during pregnancy (5,6). It is important that pregnant women are not required to attend lengthy clinic sessions for OGTTs, especially during a pandemic. Therefore, simpler yet accurate alternative screening tests should be implemented to reduce the number of OGTTs (7).

Previous research has suggested that fasting plasma glucose (FPG) can be used as a screening technique for gestational diabetes mellitus (GDM) diagnosis. FPG is easier and quicker to use, is less expensive, and can lower healthcare costs associated with universal oral glucose tolerance test (OGTT) screening. However, to accurately diagnose GDM, it is necessary to evaluate the diagnostic performance and determine the ideal FPG cutoff (7). Ping et al. found that gestational diabetes mellitus (GDM) can be predicted through both pre-BMI and initial fasting plasma glucose (FPG) levels before 24 weeks (8). Similarly, Hao et al. found that women who develop GDM tend to have significantly higher FPG levels during the first trimester ( $4.6 \pm 0.3$  mmol/L) compared to women with normal glucose tolerance ( $4.4 \pm 0.3$  mmol/L;  $p=0.001$ ), as well as higher BMI during the same period (9). Additionally, Shin Y et al. reported that a higher BMI is linked to a greater prevalence of GDM. Despite a higher risk

of developing type 2 diabetes, lifestyle interventions that aim to reduce BMI have the potential to lower the risk of GDM (10). The lack of a standardized agreement on diagnostic criteria and cutoff values for screening tests of FBG and pre-BMI has made it difficult to detect women with GDM early (8). Thus, our study aims to define optimal levels of FBG for the detection of GDM.

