### **Data Collection Technique and Tool**

The data collection tool was developed and face-validated by two consultants in the field. The tool was designed to collect data from the medical records of the participants, including their fasting blood glucose (FBG) levels and oral glucose tolerance test (OGTT) results. The tool was also used to collect information about the participants' obstetric history, demographic characteristics, and medical conditions.

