### **Data Entry and Statistical Analysis**

The researchers used IBM SPSS Statistics (version 29.0) for data analysis. Categorical variables were presented as proportions, while numerical variables were presented as medians and interquartile ranges due to non-normal distribution. Inferential analyses of categorical variables were conducted using statistical tests such as chi-square and Fisher-Freeman-Halton Exact Tests. Additionally, multivariate analyses were conducted using binary logistic regression, with significance determined by p-values less than 0.05 and inferences made with a 95% confidence level.

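### The aim of an optimal FBG level has no criterion tied to sparing OGTTs, and the planned tests cannot show how many OGTTs a level avoids or how many GDM cases it misses

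*Combined protocol and SAP*

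**What the plan says.** The Introduction gives the practical motive: the OGTT is slow and poorly tolerated, so "simpler yet accurate alternative screening tests should be implemented to reduce the number of OGTTs". It also states a diagnostic motive: "to accurately diagnose GDM, it is necessary to evaluate the diagnostic performance and determine the ideal FPG cutoff". The section closes with the aim: "our study aims to define optimal levels of FBG for the detection of GDM". The Rationale adds an intention to evaluate diagnostic performance, but names no measure of it.

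Under Data Collection Technique and Tool, the items taken from the records are described as "including their fasting blood glucose (FBG) levels and oral glucose tolerance test (OGTT) results". The time in pregnancy at which FBG was measured is not given.

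The analysis is set out under Data Entry and Statistical Analysis: "Inferential analyses of categorical variables were conducted using statistical tests such as chi-square and Fisher-Freeman-Halton Exact Tests", and "multivariate analyses were conducted using binary logistic regression, with significance determined by p-values less than 0.05". No section names a cutoff rule, a ROC analysis, sensitivity, specificity, a predictive value, or a count of OGTTs avoided.

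**The concern.** Whether FBG can spare women an OGTT depends on two quantities at a given level: the share of women who would skip the test, and the number of GDM cases among them. The aim mentions neither. The listed methods, as described, test whether variables are associated with GDM. A small p-value or an odds ratio for FBG does not say how many OGTTs a level saves or what the saving costs.

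Adding a ROC curve would not be enough. With no criterion declared, the level could be chosen after looking at the curve, and different reasonable criteria give very different trade-offs. The study could then publish an optimal level that readers take as a substitute for the OGTT without seeing how many cases it leaves undetected.

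**Working it through.** The plan states no cutoff, accuracy figure or sample size, so there is no figure of its own to reproduce. The calculation below only shows how much the choice of criterion can matter. The levels in it are not proposals.

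**Inputs from the documents.** The Introduction cites a study in which "women who develop GDM tend to have significantly higher FPG levels during the first trimester": 4.6 ± 0.3 mmol/L, against 4.4 ± 0.3 mmol/L with normal glucose tolerance.

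**Assumptions not in the documents.** The ± value is an SD (it is not labelled). FBG is normal with the same SD in both groups. GDM prevalence is 25%, with a range shown below. Women below the level get no OGTT.

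**Separation.** AUC = Φ(0.2 / (0.3 × √2)) = 0.68.

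**Balanced level (maximum of sensitivity + specificity).**
- Level = (4.6 + 4.4) / 2 = 4.5 mmol/L.
- Sensitivity = specificity = Φ(0.1 / 0.3) = 0.631, so 36.9% of GDM is missed.
- OGTTs avoided = 0.25 × 0.369 + 0.75 × 0.631 = 0.565, about 57%.
- Per 1,000 women: 250 × 0.369 = 92 cases missed.

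**Level with 90% sensitivity.**
- Level = 4.6 − 1.2816 × 0.3 = 4.22 mmol/L.
- Specificity = Φ((4.216 − 4.4) / 0.3) = 0.269.
- OGTTs avoided = 0.25 × 0.10 + 0.75 × 0.269 = 0.227, about 23%.
- Per 1,000 women: 250 × 0.10 = 25 cases missed.

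**How firm these figures are.**
- *Rounding of the printed values, common SD.* With means 4.65 and 4.35 and SD 0.25, the balanced level misses Φ(−0.15 / 0.25) = 27%. With means 4.55 and 4.45 and SD 0.35, it misses Φ(−0.05 / 0.35) = 44%. In the same two cases the 90%-sensitivity level has specificity Φ(1.2 − 1.2816) = 0.467 and Φ(0.286 − 1.2816) = 0.160. It then avoids 0.025 + 0.75 × 0.467 = 38% and 0.025 + 0.75 × 0.160 = 14% (0.145 before rounding) of OGTTs.
- *SDs that differ within rounding.* The balanced level misses 19% to 64%.
- *Lognormal shape.* The balanced level is 4.47 mmol/L and misses 34%.
- *Prevalence 10% to 30%.* The balanced level avoids 60% to 55% of OGTTs, and the 90%-sensitivity level avoids 25% to 22%.

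**The case against.** A reader might infer that the plan has chosen the wrong target, namely a balanced cutoff unusable for deciding who can skip the OGTT. The documents do not support that. No section mentions a balanced or Youden point. The word optimal could cover a high-sensitivity rule-out level, and the plural in the aim is compatible with two levels. Sparing OGTTs is also not the only purpose: the Introduction stresses early detection and accurate diagnosis, and the aim follows directly from a sentence about the lack of agreed cutoffs for detecting GDM early.

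It would also be wrong to call 37% the protocol's own figure. It is derived from background results of a first-trimester study. The Introduction places the diagnostic OGTT at 24 to 28 weeks, this study's FBG timing is unstated, and its patients come from high-risk clinics. The plan reports its own numerical variables as non-normal.

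Nor does a balanced point value a missed case and an unneeded OGTT equally. It gives equal weight to the two rates, which implies a cost ratio of (1 − p) / p. At 25% prevalence that is 0.75 / 0.25 = 3 false positives to one missed case.

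Finally, cases are missed only if women below the level go untested, and the plan does not say that they would. If OGTTs were spared the other way, by labelling women above 4.5 mmol/L as GDM, the same model gives 750 × 0.369 = 277 false positives per 1,000 against 250 × 0.631 = 158 true cases, a positive predictive value of 158 / 435 = 36%. An undefined criterion therefore matters under either use.

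All these limits stand. They leave untouched the fact that no criterion is stated and no listed analysis yields the two quantities that the OGTT-sparing motive needs.

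**Conclusion.** The point holds as a missing criterion and a missing analysis. The aim is not tied to any rule for choosing a level, and the listed methods cannot show what a level would save or cost. In the illustration, moving from a balanced level to one with 90% sensitivity cuts missed cases from 92 to 25 per 1,000 women and OGTTs avoided from about 57% to about 23%. The size rests on the assumptions listed with the calculation and on another study's data, so it shows only that the choice is consequential. It does not forecast this study's accuracy. Making triage the sole aim, or demoting a balanced level to secondary status, would be a matter of preference. The change is a cheap improvement that would let the study address its OGTT-sparing motive.

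**What to change.** In the aim at the end of the Introduction, state the intended use of the FBG level: ruling out the need for an OGTT, detecting GDM, or both.

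Under Data Entry and Statistical Analysis, add an accuracy analysis of FBG against the OGTT result. Declare and justify a minimum sensitivity, chosen by the investigators. The methods are written in the past tense and already report the shape of the data, so if the data have been examined, say that the criterion is post hoc.

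At the level that meets this criterion, and at any other level presented (including a balanced one), report sensitivity, specificity, OGTTs avoided per 1,000 women and GDM cases missed per 1,000 women, each with a 95% CI. State what is assumed to happen to women on each side of the level.

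The cost is some wording and one extra table from FBG and OGTT data already in the collection tool. The downside is a headline that may look less favourable.

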## **Rationale**

The aim of this study is to examine potential risk factors and complications linked to high-risk pregnancies, with a specific focus on gestational diabetes mellitus (GDM). The study intends to offer an understanding of the relationship between GDM and factors such as impaired fasting glucose or impaired glucose tolerance (IFG/IGT), family history of diabetes mellitus (DM), and medical conditions. The study also intends to evaluate the diagnostic performance of screening techniques for gestational diabetes mellitus (GDM), including a history of GDM and impaired fasting glucose (IFG) or impaired glucose tolerance (IGT).

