## **Methods and materials**

### **Study design and area**

This study was a hospital-based retrospective cross-sectional study. The study was conducted at the clinic of King Abdul-Aziz Medical City, a tertiary care hospital in Jeddah, Saudi Arabia. Data were collected from the target population through the use of medical records.

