### **Sampling technique and size**

The sampling technique for this study is non-probability consecutive sampling, which will include all pregnant patients who visited high-risk pregnancy outpatient clinics at King Abdul-Aziz Medical City in Jeddah from 2021 to 2022. The study aims to collect data from all members of the target population instead of sampling from a larger population.

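### The plan aims to define an optimal FBG level from one record set but provides no internal validation and no interval for the cut-off; accuracy assessed in the same women would be optimistic

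*Combined protocol and SAP*

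**What the plan says.** The aim at the end of the Introduction is that "our study aims to define optimal levels of FBG for the detection of GDM". Earlier in that section, as background to the use of fasting glucose for screening, the text says that "it is necessary to evaluate the diagnostic performance and determine the ideal FPG cutoff".

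There is one source of data. Under Study design and area: "This study was a hospital-based retrospective cross-sectional study". Under Sampling technique and size: "The study aims to collect data from all members of the target population instead of sampling from a larger population". No second cohort, hold-out set or split is described, and neither the number of women nor the number of GDM cases is given.

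The Data Entry and Statistical Analysis section lists proportions, medians and interquartile ranges, and then: "Inferential analyses of categorical variables were conducted using statistical tests such as chi-square and Fisher-Freeman-Halton Exact Tests". It adds binary logistic regression, a 0.05 significance threshold and "inferences made with a 95% confidence level". It names no rule for choosing a cut-off, no sensitivity, specificity or ROC measure, no resampling and no interval for a cut-off.

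**The concern.** An optimal level has to be found by searching the data. A search for the best-looking threshold picks up chance features of the sample along with the real separation between groups. Sensitivity and specificity read off in the same women therefore tend to be too favourable. With a single record set and no validation step, the plan describes no other place where the chosen level could be assessed.

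The Introduction presents fasting glucose as a way to spare women the OGTT. If sensitivity at the chosen level were overstated, a clinic using it would miss more GDM than the study reported. A threshold printed without an interval would also look exact when it might be poorly determined.

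The missing cut-off method is the more basic gap, but filling it with an ordinary ROC curve and Youden point would not deal with this one. That analysis produces exactly the uncorrected figures. The correction has to be specified as well.

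**Working it through.** The documents state no cut-off, AUC, sensitivity, specificity or sample size, so there is no planned figure to reproduce. The check is an illustration of size.

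**Inputs from the documents.** Fasting glucose 4.6 (SD 0.3) mmol/L in women who developed GDM and 4.4 (SD 0.3) in women with normal tolerance, from the first-trimester study cited in the Introduction.

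**Assumptions.** Normal distributions; cut-off chosen to maximise the Youden index J = sensitivity + specificity − 1; values recorded to 0.1 mmol/L; case numbers as shown below.

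**True performance of the marker.**
- Standardised difference d = (4.6 − 4.4)/0.3 = 0.667.
- AUC = Φ(d/√2) = Φ(0.471) = 0.681.
- Best cut-off = midpoint = 4.5 mmol/L, where sensitivity = specificity = Φ(d/2) = Φ(0.333) = 0.631.
- Best possible J = 2 × 0.631 − 1 = 0.261 (unrounded inputs).

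**Simulation.** In each of 2,000 or more simulated datasets per size, the cut-off with the highest J in the sample was selected. Its apparent J was compared with the true J at that cut-off, computed from the normal distributions. Optimism is the mean apparent J minus the mean true J.

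| GDM / non-GDM | Apparent J | True J | Optimism in J | Sensitivity too high by (points) | Chosen cut-off, 5th–95th percentile (mmol/L) |
|---|---|---|---|---|---|
| 25 / 75 | 0.316 | 0.236 | 0.080 | about 6 | 4.3–4.8 |
| 100 / 400 | 0.279 | 0.249 | 0.030 | about 2.5 | 4.4–4.7 |
| 200 / 800 | 0.271 | 0.253 | 0.018 | about 1.5 | 4.4–4.7 |
| 1,000 / 4,000 | 0.263 | 0.257 | 0.006 | about 0.5 | 4.5–4.6 |

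**Recording precision.** Finer recording gives more candidate cut-offs and more optimism. At 20% prevalence, recording to 0.01 rather than 0.1 mmol/L changes the optimism in J from 0.092 to 0.118 with 100 women, from 0.028 to 0.045 with 500, from 0.017 to 0.030 with 1,000 and from 0.006 to 0.009 with 5,000.

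**Stability of the cut-off.** With 25 cases the range has width 4.8 − 4.3 = 0.5 mmol/L, and with 100 to 200 cases 4.7 − 4.4 = 0.3. Both exceed the 0.2 mmol/L difference between the group means.

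**Ordinary intervals.** Wilson 95% intervals that ignore the selection covered the true sensitivity in 0.88 to 0.94 of datasets with 0.01 recording and 0.92 to 0.96 with 0.1 recording. For specificity, coverage was 0.925 to 0.957 overall. These figures span 100 to 5,000 women and 10% to 30% prevalence.

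**The case against.** A reader might infer that the study will choose the level and evaluate it in the same women, and that its published accuracy will therefore be too high. The documents do not say so. The analysis section names no cut-off rule and no accuracy measure. The Rationale's diagnostic-performance aim gives a history of GDM and impaired fasting glucose or glucose tolerance as its examples; these are categories, not a threshold to be searched for. The Introduction's remark about finding the ideal cut-off is background with a citation. The point is therefore conditional.

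A reader might also infer that the uncertainty would be hidden altogether. That is too strong. The plan promises inference at 95% confidence, and ordinary intervals for sensitivity and specificity lose only a few points of coverage in most scenarios. What is missing is an interval for the cut-off itself.

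The size may also be trivial. The sample takes in all eligible women over 2021–2022, and with 1,000 cases the optimism in J is 0.01 or less. The illustrative inputs come from the first trimester in another population, whereas the timing of FBG in these high-risk clinic records is not given; if it was measured at the OGTT, the separation could differ. All of this stands. It limits how large the problem can be said to be, but it does not supply a validation step. Because the number of cases is not stated, a large cohort cannot be assumed.

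Finally, the point could be folded into the absence of any cut-off analysis. The two are related, and the selection rule is common to both, but the optimism correction and the interval for the cut-off would not follow from repairing that gap alone.

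**Conclusion.** The concern holds in conditional form. The plan sets out to define an optimal FBG level from one record set, with no internal validation and no interval for the cut-off. If that level is evaluated in the women used to choose it, apparent accuracy will be biased upward. The direction was the same in every scenario examined. The size runs from material with about 25 cases to negligible with about 1,000, and the documents do not allow it to be fixed more closely. The figures rest on the cited means and SDs, normality, the Youden rule and the assumed case numbers and recording precision. The documents do not support a claim that the reported accuracy is certain to be overstated by any particular amount.

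**What to change.** Add to the Data Entry and Statistical Analysis section:

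- One rule for selecting the cut-off, fixed before the data are searched (for example the maximum Youden index, or a stated minimum sensitivity). The text is written in the past tense; if a cut-off has already been selected, say so and do not present the rule as prespecified.
- A bootstrap of the whole selection step, for example 1,000 resamples, with the cut-off re-selected in each.
- Optimism-corrected sensitivity and specificity at the chosen cut-off, reported next to the apparent values.
- A bootstrap 95% interval for the cut-off itself.
- The number of women and of GDM cases that contribute, so that readers can judge the likely optimism.

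The cost is a few lines of text and a short additional analysis of existing data. The accuracy figures will look slightly less favourable and the intervals will be wider. If the cohort is large, the bootstrap will show that the correction is small.

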## **Rationale**

The aim of this study is to examine potential risk factors and complications linked to high-risk pregnancies, with a specific focus on gestational diabetes mellitus (GDM). The study intends to offer an understanding of the relationship between GDM and factors such as impaired fasting glucose or impaired glucose tolerance (IFG/IGT), family history of diabetes mellitus (DM), and medical conditions. The study also intends to evaluate the diagnostic performance of screening techniques for gestational diabetes mellitus (GDM), including a history of GDM and impaired fasting glucose (IFG) or impaired glucose tolerance (IGT).

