### **Study Population**

For this study, we looked at all pregnant patients who visited high-risk pregnancy outpatient clinics at King Abdul-Aziz Medical City in Jeddah from 2021 to 2022. Our focus was on singleton pregnant women who received prenatal care services in Obstetrics clinics at King Abdul-Aziz Medical City. However, to ensure accurate and valid results, we excluded pregnant women with diabetes mellitus or autoimmune diseases. By examining this specific

population of pregnant women, we aimed to investigate potential risk factors and complications associated with high-risk pregnancies.

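### Does listing complications as an aim, with no outcome, delivery window or model for them, call for a change to the plan?

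*Combined protocol and SAP*

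**What the plan says.** The aim appears twice. The Rationale begins with "The aim of this study is to examine potential risk factors and complications linked to high-risk pregnancies" and adds that GDM is the particular focus. The Study Population section closes by saying "we aimed to investigate potential risk factors and complications associated with high-risk pregnancies". The end of the Introduction gives a different aim: "Thus, our study aims to define optimal levels of FBG for the detection of GDM". The Rationale adds a further one, the diagnostic performance of screening techniques.

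The methods describe a retrospective cross-sectional study from medical records. The Sampling technique and size section "will include all pregnant patients who visited high-risk pregnancy outpatient clinics" in 2021 to 2022. The Data Collection Technique and Tool section mentions fasting glucose and OGTT results, together with "obstetric history, demographic characteristics, and medical conditions". The Data Entry and Statistical Analysis section names chi-square and Fisher-Freeman-Halton tests, and then says that "multivariate analyses were conducted using binary logistic regression, with significance determined by p-values less than 0.05". It gives no dependent variable.

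**The concern.** An aim normally needs an outcome, a period over which that outcome is ascertained, and an analysis. For complications the plan supplies none of the three. The Introduction uses the word for what GDM does to mother and child ("It can lead to a range of complications for both the mother and the baby"), so a reader may expect results on macrosomia, neonatal hypoglycaemia and the like.

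There is also a question of time order. Obstetric history is not divided into events before and events during the index pregnancy. An event before it can predict GDM in this pregnancy but cannot result from it. With an open category, an unnamed dependent variable and complications among the aims, an association with an earlier event might be reported as though it were a consequence of GDM. At stake would be one of at least four stated objectives: the fasting-glucose cutoff, risk factors, complications, and diagnostic performance.

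**Working it through.** The plan gives no sample size, event count or complication rate, so there is no figure of its own to reproduce. The check is a comparison of sections.

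**What the aim can mean.** Both statements attach complications to high-risk pregnancies, not to GDM.

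- *Reading A: GDM is the complication.* The next sentence of the Rationale relates GDM to impaired fasting glucose or glucose tolerance, family history of diabetes, and medical conditions. Nothing downstream of GDM is listed. A cross-sectional design fits this reading, because it promises no follow-up to delivery. The aim then reduces to risk factors for GDM, and the extra word is loose drafting.
- *Reading B: complications are consequences of GDM.* This draws on the Introduction, which is background. Specific consequences are named only there and in reference titles, never as study variables.

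**What the methods supply under Reading B.**

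| Element | Where one would look | What is there |
|---|---|---|
| Outcome | Data Collection Technique and Tool | None named beyond glucose testing; the record items are introduced as inclusions, and the tool is not reproduced |
| Window | Study design, Study Population, Sampling | Entry by clinic visit in 2021 to 2022; no end date for record review |
| Model | Data Entry and Statistical Analysis | Tests and regression named; no dependent variable for any aim |

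One of the five methods sections (Study Population) mentions complications, and only as an aim. The gap is real, but each row shows something left unstated. None shows that a complication was excluded or analysed wrongly. The missing dependent variable is a general feature of the analysis section and is not peculiar to this aim.

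**Can the effect be sized?** One could ask what share of women would deliver after the visit period closes. The two-year period is 730/7 = 104.3 weeks. Assume testing at 24–28 weeks (the Introduction cites this as an international recommendation; the methods do not state test timing), delivery at 37–41 weeks, tests spread evenly, and record review ending on 31 December 2022.

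- Low: (37 − 28)/104.3 = 9/104.3 = 8.6%.
- High: (41 − 24)/104.3 = 17/104.3 = 16.3%.

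The arithmetic is right, but the last assumption has no support: the period defines entry, and no section closes record review on that date. On the same assumptions the latest delivery is 17 weeks later, about 29 April 2023. Three references carry access dates of 1 September 2023. Those dates do not fix when records were abstracted, but they make abstraction after April 2023 plausible, and the share lost would then be 0%. A range from 0% to 16.3%, set by an unstated date, says nothing useful about this plan.

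**The case for a change.** The strongest case for a change is that the text needs correcting on either reading. If GDM is the complication, the word adds nothing and can go. If consequences are meant, the aim lacks an outcome. The repair is cheap: edit two sentences, and add a rule that events before the index pregnancy are reported only as predictors. Because it governs claims and needs no new data, it would work even in a completed retrospective study.

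Part of this stands. The wording is loose, it occurs in two places, and a clarified aim would read better. The time-order point is also correct in principle: an earlier event cannot be a consequence of the index GDM.

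What does not stand is the step to a needed change. No section proposes to report obstetric history as an effect of GDM, so the feared misreporting is conjecture. The suggested rule states what a competent analyst would do unprompted. Deleting the word alters no variable, test, model or estimate. The only remedy that would alter an analysis is to name delivery and neonatal outcomes, extend the window and model GDM as an exposure. That would need renewed record abstraction, and the documents do not show that delivery data are available.

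**Conclusion.** The observation is accurate and the inference from it is too strong. The plan does not specify any maternal or neonatal outcome of the index pregnancy other than GDM, a window to delivery, or a model for such an outcome. That is missing detail around an ambiguous word. It is not a rule that produces a wrong answer, and it does not show that complications were left out of the data or the analysis.

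No change to the plan is called for. The point affects the wording of one of at least four objectives; the fasting-glucose cutoff and diagnostic-performance aims are untouched, and no numerical effect can be derived from the documents. This rests on two assumptions: that analysts keep events before the index pregnancy on the predictor side, and that no conclusion about consequences of GDM is drawn without a named outcome and its ascertainment period. A report that did draw such a conclusion would deserve challenge on its own terms.
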